8.3.6. C-SSRS Assessment

The C-SSRS assessment will be administered at all study visits. The Baseline version will be used at Visit 1 for all subjects. For Visits 2 through 5, the Since Last Visit version will be used. Any subject with a positive score at on the Baseline version or an appearance of any new suicidal ideation or suicide behavior since the Baseline version should be referred to their primary care provider for follow-up.

If a subject has any post-Screening C-SSRS score of 1-3 for Ideation (i.e., a "yes" answer to Questions 1, 2, or 3) or a "yes" response to the Non-Suicidal Self-Injurious Behavior question) and the score is higher than the Screening C-SSRS score, then this assessment should be recorded as an AE. This information is reported as indicated in Section 9. (Possible AE terms: Suicidal plans, Suicidal ideation, Suicidal tendency, Suicidal behavior, Suicidal intention, Suicidal depression, Active suicidal ideation, Passive suicidal ideation, Self-injurious behavior without suicidal intent).

If a subject has any post-Screening C-SSRS score of 4 or 5 for Ideation (i.e., a "yes" answer to question 4 or 5) and/or any questions answered yes for Suicidal Behavior (with the exception of a "yes" response to the Non-Suicidal Self-Injurious Behavior question), and this was not observed at Screening, then this assessment should be recorded as a Serious Adverse Event (SAE). This information is reported as indicated in Section 9.2.2.

9. ADVERSE EVENT REPORTING

Timely, accurate, and complete reporting and analysis of safety information from clinical trials will be conducted in accordance with Good Clinical Practice.

All AEs, including serious adverse events (SAEs) reported or observed during or after dosing with the study drug will be recorded on the AE page of the eCRF for all enrolled subjects. Information to be collected includes description of event, date of onset, investigator-specified assessment of the severity and relationship to study drug, date of resolution of the event, seriousness, any required treatment or evaluations, and outcome. Adverse events resulting from concurrent illnesses, reactions to concurrent medications, or progression of disease states must also be reported. Perforations of the tympanic membrane will be captured as AEs only if the perforation increases in size and does not resolve by the end of the study.

If the existing medical condition worsens at any time after application of study drug, it should be recorded as an AE.

9.1. Adverse Event Classification Definitions

Adverse Event:

An AE is any unfavorable and unintended diagnosis, symptom, sign, syndrome or disease which occurs during the study, having been absent at baseline, or, if present at baseline, appears to worsen.

This includes any occurrence that is new in onset or aggravated in severity or frequency from the baseline condition, including abnormal results of diagnostic procedures and/or laboratory test abnormalities, which are considered AEs if they:

- result in discontinuation from the study
- require treatment or any other therapeutic intervention
- require further diagnostic evaluation (excluding a repetition of the same procedure to confirm the abnormality)
- are associated with clinical signs or symptoms judged by the investigator to have a significant clinical impact

Serious Adverse Event (SAE):

An SAE is defined as any untoward medical occurrence that:

- results in death,
- is life-threatening (Note: the term "life-threatening" refers to an event in which the subject was at risk of death at the time of the event rather than to an event which hypothetically might have caused death if it were more severe.),
- requires in-patient hospitalization or prolongation of existing hospitalization,
- results in persistent or significant disability/incapacity, or

• is a congenital anomaly/birth defect.

Medical and scientific judgment should be exercised in deciding whether expedited reporting is appropriate in other situations, such as important medical events that may not be immediately life-threatening or result in death or hospitalization but may jeopardize the subject or may require intervention to prevent one of the other outcomes listed in the above definition. These events should be considered serious.

9.1.1. Assessment of Severity

The investigator will assess the intensity of the AE and rate the AE as mild, moderate, or severe using the following criteria:

Grade 1 – Mild: These events are easily tolerated, require minimal or no treatment, and do not interfere with the subject's daily activities.

Grade 2 – Moderate: These events cause sufficient discomfort to interfere with daily activity and/or require a simple dose of medication, e.g., analgesics or anti-emetics.

Grade 3 – Severe: These events incapacitate and prevent usual activity or require complex medication/treatment or hospitalization.

Grade 4 – Life Threatening: These events are those for which the subject was at risk of death at the time of the event rather than an event which hypothetically might have caused death if it were more severe.

Grade 5 – Death: The event resulted in the death of the subject.

Changes in the severity of an AE should be documented to allow for an assessment of the duration of the event at each level of intensity to be performed.

9.1.2. Assessment of Causality

The investigator's assessment of an AE's relationship to study drug will be part of the documentation process, but will not be a factor in determining what is or is not reported in the study.

The investigator will assess the relationship or association of the study drug in causing or contributing to the AE, which will be characterized using the following classification and criteria:

Definite: Adverse events that, after careful medical evaluation, are considered definitely related to the study drug; other conditions (concurrent illness, progression/expression of disease state, or concurrent medication reaction) do not appear to explain the event.

Probable: Adverse events that, after careful medical evaluation, are considered with a high degree of certainty to be related to the study drug. The following characteristics will apply:

- a reasonable temporal relationship exists between the event and exposure to the study drug, and
- the event is a known reaction to the study drug that cannot be explained by an alternative cause commonly occurring in the population/individual, or

• the event is not a known reaction to the study drug but cannot be reasonably explained by an alternative cause.

Possible: Adverse events that, after careful medical evaluation, do not meet the criteria for a definite or probable relationship to the study drug, but for which a connection cannot be ruled out with certainty. The following characteristics will apply:

- the event occurs after exposure to the study drug, and
- there is a reasonable temporal relationship to the application, but the event is not a known reaction to the study drug and could be explained by a commonly occurring alternative cause, or
- in the absence of a reasonable temporal relationship, the event cannot be explained by an alternative cause.

Not related: Adverse events in this category will have either of the following characteristics:

• the event does not have a reasonable temporal relationship to study drug administration and/or can be explained by a commonly occurring alternative cause.

9.1.3. Follow up of Adverse Events

The investigator will follow a non-serious AE until resolution, stabilization, or the End of Study Visit. The investigator will follow an SAE (regardless of relationship to study drug) until the event resolves, stabilizes, or becomes non-serious. All AEs identified on the last scheduled contact must be recorded on the AE page of the eCRF and the current status (ongoing or resolved) will be noted. In addition, SAEs will be reported to Product Safety according to the reporting guidelines identified in Section 9.2.2.

9.2. Monitoring of Adverse Events

9.2.1. All Adverse Events

All AEs will be analyzed for safety. Those meeting the definition of SAE must be reported using the SAE Form. Subjects should voluntarily report any AEs or report AEs in response to general, non-directed questioning (e.g., "How has your health been since the last visit?"). For each AE volunteered by the subject, the investigator should obtain all the information required to complete the AE page of the eCRF, in accordance with the guidelines that accompany it.

All AEs, regardless of seriousness, severity, or presumed relationship to study therapy, must be recorded using medical terminology in the source document and on the eCRF. Whenever possible, diagnoses should be given when signs and symptoms are due to a common etiology (e.g., cough, runny nose, sneezing, sore throat, and head congestion should be reported as "upper respiratory infection"). Investigators must record on the eCRF their opinion concerning the relationship of the AE to study therapy. All measures required for AE management must be recorded in the source document and reported according to sponsor instructions.

Any non-serious AE that occurs after the dose of study drug must be reported in detail on the appropriate eCRF page and followed until resolution, stabilization, or the End of Study Visit. The description of the AE will include description of event, date of onset, date of resolution,

investigator assessment of severity and relationship to study drug, seriousness, any required treatment or evaluations, and outcome.

The sponsor assumes responsibility for appropriate reporting of AEs to the regulatory authorities. The sponsor will also report to the investigators all serious AEs that are unlisted and associated with the use of the drug. The investigators must report these events to the appropriate Research Ethics Committee (REC) in accordance with local regulations.

9.2.2. Serious Adverse Events

All SAEs occurring during clinical trials must be reported within 24 hours to Product Safety.

The cause of death of a subject in a clinical trial, whether the event is expected or associated with the investigational agent, is an SAE.

The initial report of an SAE may be made by telephone, e-mail or facsimile (fax). The investigator must provide the minimal information: i.e., protocol number, subject's initials and date of birth, subject number or medication code number, nature of the AE and investigator's attribution.

All oral reports of an SAE must be confirmed within 24 hours by a written, more detailed report and signed by the investigator. For this purpose, the sponsor will provide the investigator with the Serious Adverse Event Form for Clinical Trials.

All SAEs that have not resolved by the end of the study, or that have not resolved upon discontinuation of the subject's participation in the study, must be followed until either:

- the event resolves,
- the event stabilizes, or
- the event becomes non-serious

The investigator should report any follow-up information as it becomes available.

9.2.3. Pregnancies

Pregnancies occurring after the first dose of investigational product and during participation of the study are considered immediately reportable events. While not considered a SAE unless a serious criterion is met, pregnancies occurring in subjects enrolled on the study must be reported and followed to outcome. The investigator should complete the pregnancy report eCRF within one working day of knowledge of the pregnancy. Following delivery or termination of pregnancy, the follow-up pregnancy report form should be completed on the pregnancy CRF. Spontaneous abortions should always be reported as SAEs. Follow-up information regarding the outcome of the pregnancy and any postnatal sequelae in the infant will be required.

9.3. Contacting Sponsor Regarding Safety

Any AE considered serious by the investigator, or that meets the SAE criteria stated in this protocol, must be reported to Product Safety within 24 hours from the time that study site personnel first learns of the event. The study site must enter the SAE into the EDC system.

Source documents will be requested from the study sites for SAEs and should be provided to Product Safety. If the subject is hospitalized during the study, a copy of the hospital discharge summary should be provided to the Product Safety as soon as it becomes available.

10. SUBJECT COMPLETION

10.1. Completion

Study subject participation is complete after Visit 5. Subjects who withdraw their consent to be followed or are lost-to-follow-up before completion of Visit 5 (Week 12) will not be considered to have completed the study.

10.2. Withdrawal

All subjects have the right to withdraw from study evaluations at any time, for any reason, without prejudice; nonetheless, investigators should attempt to encourage subjects to complete the protocol so that continued observation and follow-up measurements may be obtained. The investigator may discontinue a subject's participation in the study at his/her discretion for reasons including, but not limited to, the following:

- 1. Subject experiences a serious or intolerable AE that, in the opinion of the investigator, requires withdrawal from the study.
- 2. Subject is in violation of the protocol.
- 3. Subject develops a condition during the course of the study that makes it unwise to continue with the trial.
- 4. Subject requires a medication that is prohibited by the protocol.
- 5. Subject requests an early discontinuation for any reason.

At any point, the investigator may discontinue the subject's study participation at his/her discretion and ensure the subject receives appropriate medical care; the investigator may also consult the medical monitor to discuss out-of-range test results.

10.2.1. Handling of Withdrawals

Subjects will be free to withdraw from study drug administration and further follow-up the study at any time. Subject participation in the study may be stopped at any time at the discretion of the investigator or at the request of the sponsor.

Whenever possible, all subjects who withdraw from study drug administration should be encouraged to remain on-study for further follow-up through the subject last scheduled visit. However, should a request for early withdrawal from the study with no further follow-up be

made, the subject should be encouraged to return to the study site for a last follow up visit and undergo all end of study/early termination assessments.

When a subject withdraws from administration of study drug or the study prior to completing Visit 5 (Week 12), the reason for withdrawal is to be documented on the eCRFs and in the source document.

10.2.2. Replacements

Subjects who discontinue participation in the study for any reason after dosing will not be replaced.

11. STATISTICAL METHODS

The primary objective of this Phase 3 study is to test the hypothesis that subjects randomized to OTO-104 will demonstrate fewer definitive vertigo days (DVD) than subjects randomized to placebo at Week 12 (the 4-week (28-day) interval from Week 9 through Week 12). The secondary objective of the study is to describe the safety profile of a 12 mg dose of OTO-104 compared to placebo when administered as a single intratympanic injection in subjects with Meniere's disease.

The following statistical sections describe the general analytic methods to be implemented to assess the overall study objectives. More detailed descriptions of the methodology will be provided in the Statistical Analysis Plan (SAP). The SAP will be prepared and finalized before unblinding the subjects' randomized treatment assignments.

11.2. Analysis Sets

The following definitions will be used to derive the analysis sets for this study.

Full Analysis Set (FAS): The full analysis set will include all subjects who are randomized, receive study drug, have a baseline definitive vertigo measurement for the 4-week lead-in period and at least one 4-week definitive vertigo measurement post-baseline. The primary analysis for the primary endpoint of DVD will be conducted using the FAS. Subjects will be included in the treatment group to which they were randomized regardless of the actual study drug received.

Completers Analysis Set: The completers analysis set will include all subjects who are randomized, receive study drug, and have all baseline and post-baseline definitive vertigo measurements for each 4-week study interval. Subjects will be included in the treatment group to which they were randomized regardless of the actual study drug received.

Per Protocol Analysis Set: The per protocol analysis set will include all subjects who are randomized, receive study drug, meet eligibility criteria, have no major protocol deviations, and have a baseline and at least one 4-week definitive vertigo measurement post-baseline. Subjects will be included in the treatment group of the actual study drug received.

Intent-to-Treat Analysis Set (ITT): The ITT analysis set will include all randomized subjects who receive study drug. Subjects will be included in the treatment group to which they were randomized regardless of the actual study drug received.

Safety Analysis Set: The safety analysis set will include all subjects who receive study drug. Subjects will be included in the treatment group according to the actual treatment received regardless of their randomized assignment. When the ear is the unit of analysis, the safety analysis will categorize an ear by whether it was a treated or an untreated ear, irrespective of whether it was the affected ear.

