5.3. Blinding

The study will be double-blinded. To maintain the blind for site personnel involved in study assessments, the following procedures will be followed:

Treatment syringes will be pre-loaded by an unblinded QMP. Each syringe will be prepared according to the detailed instructions in the Pharmacy Binder in a manner that prevents visualization of syringe contents by all other study staff through the use of a syringe overlabel. In addition, any interaction with subjects with regard to the collection, review or discussion of study assessments, with the exception of otoscopic exams, will be done by the study coordinator, audiologist or someone other than the QMP who prepared the syringe and the physician who administered the intratympanic injection of study drug. Every effort should be made to ensure that otoscopic exams are conducted by the physician who administered the study drug or another physician involved in the study, but not responsible for other assessments for the specific subject. Physicians administering study drug and conducting the otoscopic exams will be instructed not to discuss any potential visual differences observed in study material with subjects or study staff.

The blind should be broken only if knowing the subject's treatment allocation would facilitate specific emergency treatment. The physician who administered the study drug is unblinded at the time of injection. If the physician who administered the study drug is not available or does not recollect the treatment administered, the investigator can access the unblinded drug accountability records completed and retained by the QMP when preparing OTO-104 or placebo. In all cases, the investigator must contact the medical monitor as soon as is practical after unblinding has occurred and treatment initiated.

If the blind is broken, the subject will continue to be followed and evaluated per-protocol. The date, time, and reason for the unblinding must be documented on the appropriate page of the eCRF.

The randomization schedule or blocking factor(s) will not be revealed to study subjects, investigators, clinical staff, site managers or Sponsor representatives until all subjects have completed the trial and the database has been finalized by Otonomy.

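### The set named Intent-to-Treat requires dosing, as does every other set, so no planned analysis includes all randomized subjects and the ITT sensitivity analysis cannot check the FAS for selective non-dosing

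*Combined protocol and SAP*

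**What the plan says.** Section 11.2 of the protocol defines five analysis sets, and receipt of study drug is a condition of each:

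- Full Analysis Set (primary): "The full analysis set will include all subjects who are randomized, receive study drug, have a baseline definitive vertigo measurement for the 4-week lead-in period", plus at least one post-baseline 4-week measurement.
- Completers: "The completers analysis set will include all subjects who are randomized, receive study drug, and have all baseline and post-baseline definitive vertigo measurements".
- Per Protocol: "The per protocol analysis set will include all subjects who are randomized, receive study drug, meet eligibility criteria, have no major protocol deviations".
- Intent-to-Treat: "The ITT analysis set will include all randomized subjects who receive study drug".
- Safety: "The safety analysis set will include all subjects who receive study drug".

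Elsewhere the protocol fixes its population at randomization. Section 11 states the hypothesis for subjects randomized to each arm, Section 11.1 counts 160 randomized subjects, and Section 5.2.2 treats a subject as enrolled once randomized. The notes to Table 1 place randomization before administration.

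Section 11.5.4 lists the ITT set, with the per-protocol and completers sets, as a sensitivity analysis of the primary endpoint.

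Section 10.2.1 says that, whenever possible, "all subjects who withdraw from study drug administration should be encouraged to remain on-study for further follow-up through the subject last scheduled visit".

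On who knows the arm, Section 5.3 has an unblinded qualified medical professional load the syringe. It adds: "The physician who administered the study drug is unblinded at the time of injection".

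**The concern.** A sensitivity analysis is useful when it relaxes a restriction of the primary analysis. The restriction that matters here is dosing, an event after randomization, and the ITT set keeps it. The ITT set relaxes only the FAS's measurement requirements. If non-dosing differed between arms in a way related to prognosis, the FAS and ITT results would both be affected, and their agreement would give no reassurance on that point.

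Leaving out undosed subjects is usually easy to defend when everyone who could influence dosing is blind. That defence is incomplete here. The preparer opens a two-vial kit for active or a one-vial kit for placebo (Section 12.1) between randomization and injection, and the physician is unblinded at injection.

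There is also a mismatch between data collection and analysis. With a single injection, a subject who withdraws from study drug administration and stays on study is in practice one who was not injected. Section 10.2.1 encourages sites to keep such subjects on study, but any diaries they provide would enter no analysis.

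**Working it through.** **1. Membership of the sets.** Take a subject who is randomized, not injected, and stays on study with diaries through Week 12. Applying Section 11.2, the subject fails the dosing condition in the FAS, completers, per-protocol, ITT and safety sets. That is normal for a safety set, but it contradicts the name of an ITT set. Relative to the FAS, the ITT set adds only dosed subjects who lack a baseline or post-baseline measurement.

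**2. The plan's own power figure.** Inputs from Section 11.1: 80 per arm, two-sided alpha 0.05, difference 2.2, residual variance 5.0, Phase 2b means 4.5 and 2.1. The text attaches 4.5 to OTO-104, which conflicts with its stated difference (active minus placebo) of -2.4, so 4.5 is taken here as the placebo mean. The planned active mean is then 4.5 - 2.2 = 2.3. Reading 5.0 as the Pearson scale factor of the over-dispersed Poisson model:

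- z = ln(4.5/2.3) / sqrt[(5/80)(1/4.5 + 1/2.3)] = 0.671/0.2026 = 3.312
- power = Phi(3.312 - 1.960) = 91.2%

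This agrees with the stated figure of more than 90%. It depends on that reading. If 5.0 were a normal residual variance, power would be above 99.9%; if it were a standard deviation, 79.5%.

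**3. Effect of including undosed subjects.** The protocol gives no undosed rate. Assume that k of 80 active subjects are undosed and have the placebo mean. The active mean becomes 2.3 + (k/80) x 2.2, and the difference falls by (k/80) x 2.2. Power uses the formula in step 2.

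| k undosed of 80 active | Fall in difference (days) | Difference | Power of an all-randomized analysis |
|---|---|---|---|
| 0 | 0 | 2.20 | 91.2% |
| 1 | 0.03 | 2.17 | 90.4% |
| 2 | 0.06 | 2.15 | 89.6% |
| 4 | 0.11 | 2.09 | 87.9% |
| 5 | 0.14 | 2.06 | 86.9% |

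For k = 5: z = ln(4.5/2.4375) / sqrt[(5/80)(1/4.5 + 1/2.4375)] = 0.6131/0.1988 = 3.084, and Phi(3.084 - 1.960) = 86.9%. These powers concern the sensitivity analysis only; keeping the FAS as primary leaves primary power as planned.

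**4. Effect of selective exclusion.** Step 3 measures dilution, not bias. As an illustration of bias, suppose 2 of 80 subjects in one arm are left undosed and would have averaged 5 to 10 definitive vertigo days more than the other 78. Dropping them lowers that arm's mean by 2 x 5/80 = 0.125 to 2 x 10/80 = 0.25 days, against a planned difference of 2.2. Both the count and the excess are assumptions.

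**The case against.** The strongest case on the other side is that very few subjects are likely to be affected. Section 5.2.2 allows randomization only after all prerequisites are met and the scheduled Day 1 procedures are done, and Section 8.1.3 puts randomization and injection at the same visit. Zero undosed subjects is compatible with the text. The fix also leaves the primary analysis alone, and Section 11.7 leaves room for further sensitivity analyses in the SAP. All of this stands, and it limits the weight of the point. It does not make the set correct as labelled, and Section 11.2 does not defer its definitions to the SAP.

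A reader might infer more than the documents support:

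- **That undosed subjects are dropped by staff who know the arm.** Personnel who receive the randomization notification are blinded (5.2.2), and the syringe contents are masked from everyone but the preparer (5.3). Before injection only the preparer knows the arm, and nothing gives the preparer a say in whether a subject is injected. A subject may also leave before anyone knows.
- **That selective non-dosing could not be detected.** Section 10.2.1 requires the reason for withdrawal to be recorded, and 11.4 plans a disposition summary, although it does not say by arm. Counts could be recovered, but they would not correct the estimate.
- **That diaries from undosed subjects will exist.** Section 10.2.1 only encourages follow-up.
- **That partially injected subjects are excluded.** They have received study drug and can enter the sets.
- **That undosed subjects may be replaced.** Section 10.2.2 says only: "Subjects who discontinue participation in the study for any reason after dosing will not be replaced". Silence about undosed subjects is not permission, and any added subject would be randomized through the same blocked system.
- **That the arms are not compared as randomized.** The FAS, completers and ITT sets all keep the randomized arm. What is missing is a set containing every randomized subject.

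**Conclusion.** The point holds. All five sets condition on dosing, the ITT set does not match its name, and the ITT sensitivity analysis cannot test the FAS for selective non-dosing. The protocol does not show that selective non-dosing is likely; it shows that blinding does not rule it out and that no planned efficacy analysis is free of it.

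The size is small. Under an assumed 1 to 5 undosed of 80 active subjects who behave like placebo, inclusion moves the difference by about 0.03 to 0.14 days out of 2.2. The selective-exclusion illustration gives a shift of about 0.13 to 0.25 days. Neither would overturn an effect of the planned size. The change is still worth making before unblinding, because the set is wrong as named and correcting it costs little.

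**What to change.** In Section 11.2 and the SAP, define the ITT set as all randomized subjects, analysed in the arm to which they were randomized whether or not they were injected. Use whatever Week 9-12 diary entries exist, and the imputation rule that Section 11.5.4 assigns to the SAP where there are none. For uninjected subjects, count the weeks from the randomization visit. Little new method is needed. The present ITT set can already contain subjects with no Week 9-12 diary, and inclusion criteria 10 and 11 give every eligible randomized subject a lead-in count for the covariate.

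Keep the FAS as the primary set. In the disposition table (11.4), report by arm the number randomized but not dosed, with reasons. Renaming the set would correct the label but would still leave no analysis of all randomized subjects.

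The cost is protocol and SAP wording, a slightly diluted ITT estimate, and a few imputed subjects.
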